**Table TTT. Hematology over Time** 

	Placebo	4P004	4P004	4P004	4P004	4P004
	(pooled)					(pooled)
	(N=XX)	(N=XX)	(N=XX)	(N=XX)	(N=XX)	(N=XX)
Erythrocytes (tera/L)						
Baseline						
Value						
n	XX	XX	XX	XX	XX	XX
mean (SD)	XX (XX)					
()						
PCSA						
≤ 95 + decrease from baseline ≥ 20	XX (XX.X%)					
≥ 160 + increase from baseline ≥ 20	XX (XX.X%)					
No PCSA	XX (XX.X%)					
Visit 3						
Value						
n	XX	XX	XX	XX	XX	XX
mean (SD)	XX (XX)					
()						
Change from BL						
n	XX	XX	XX	XX	XX	XX
mean (SD)	XX (XX)					
()						
PCSA						
≤ 95 + decrease from baseline ≥ 20	XX (XX.X%)					
≥ 160 + increase from baseline ≥ 20	XX (XX.X%)					
No PCSA	XX (XX.X%)					
()						

For parameters with defined PCSA, a table with PCSA only will be produced:

**Table TTT. Hematology PCSA over Time** 

	Placebo	4P004	4P004	4P004	4P004	4P004
	(pooled)					(pooled)
	(N=XX)	(N=XX)	(N=XX)	(N=XX)	(N=XX)	(N=XX)
Erythrocytes (tera/L)						
Baseline						
≤ 95 + decrease from baseline ≥ 20	XX (XX.X%)					
≥ 160 + increase from baseline ≥ 20	XX (XX.X%)					
No PCSA	XX (XX.X%)					
Visit 3						
≤ 95 + decrease from baseline ≥ 20	XX (XX.X%)					
≥ 160 + increase from baseline ≥ 20	XX (XX.X%)					
No PCSA	XX (XX.X%)					
()						

### **Table TTT. Chemistry over Time**

### **Table TTT. Chemistry PCSA over Time**

Glycemia is measured as follows:

Visit	Timepoint	Method
Screening	-	Blood
Visit 2	Pre-Dose	Blood & Glucometer
Visit 2	1h Post-Dose	Glucometer
Visit 2	2h Post-Dose	Blood
Visit 2	4h Post-Dose	Blood
Visit 2	6h Post-Dose	Glucometer
Visit 2	8h Post-Dose	Blood
Visit 2	10h Post-Dose	Glucometer
Visit 2	12h Post-Dose	Blood
Visit 2	16h Post-Dose	Blood
Visit 2	24h Post-Dose	Glucometer
Visit 3	-	Blood & Glucometer

In order to obtain one value per scheduled timepoint:

- The baseline value will be selected as the last measure before IMP injection. If there are such two measures (same time, different method), then Blood will be selected.
- Post-baseline, if there are two measures for a scheduled timepoint, Blood will be selected.
- Additional samples vs. scheduled samples will not be analyzed, unless they are the baseline.

The values will be reported over time (Baseline, 1h Post-Dose to 24h Post-Dose) with the same template as Vital Signs.

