## 3.2 Endpoints

#### 3.2.1 Primary endpoints

- Number of Adverse events (AEs), serious AEs (SAEs) (Common Terminology Criteria Adverse Events [CTC-AE]) from ICF signature to D29, including target knee pain and tenderness, erythema, swelling, local pain at injection site.
- Vital signs from D-7 to D8, ECG from D-7 to D1: Mean change, number of Potentially Clinically Significant Abnormality (PCSA), Percentage of participants with PCSA
- Laboratory changes (Red Blood Cells (RBC), White Blood Cells (WBC), Hemoglobin (Hb), platelets, alanine transaminase (ALT), aspartate transaminase (AST), glycemia, amylasemia, creatinin clearance) from D-7 to D8: Mean changes number of PCSA, Percentage of participants with PCSA.

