#### DLT is based on:

- Expert's opinion
- Any related SAE

In this study, with liraglutide, DLT will be established if any of the following occurs:

- Anaphylaxis (angioedema, hypotension, shock, bronchospasm, hypoxia, or respiratory distress),
- Hypoglycemia (blood glucose level  $\leq 2.5$  mmol/L) within 2 days after injection,
- Amylasemia  $\geq$  3ULN within 7 days after injection,
- Serious gastro-intestinal adverse event within 7 days after injection.

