#### 8.5.2 Inclusion visit, D1, full day hospitalization

During this visit (24 hours hospitalization), the Investigator will:

- review inclusion / exclusion criteria, concomitant medication (from screening),
- do physical exams, ECGs, measure vital signs as per D1-D2 Study Flowchart (section 1.2.2),
- record any AE since screening,
- put a veinous line,
- remind the participant to fill in the NRS (before any study intervention on D1) for assessing target knee pain in the previous 2 days and during the hospitalization as outlined in section 1.2.2.
- randomize the participant (performed by the pharmacist)
- take blood / urine samples for glycemia, PK and OA-related biomarkers samples as per D1-D2 Study Flowchart (section 1.2.2),
- do the IA injection (modalities given in section 6.2.2 and in the Investigator manual) of the IMP extemporaneously prepared in a vial by the pharmacist (procedure for preparation is detailed in the Pharmacy manual).
- record AEs as per D1-D2 Study Flowchart (section 1.2.2),
- monitor the participant during the coming 24 hours:
  - o on local reaction as per D1-D2 Study Flowchart (section 1.2.2)
  - o on blood sugar level (veinous / capillary measures):
    - after IMP injection, glycemia will be systematically monitored (capillary measures via glucose meter and/or veinous measures) as per D1-D2 Study Flowchart (section 1.2.2),
    - when planned measurement indicates glycemia is ≤ 70 mg/dL without clinical symptom repeat the test each 30 min up to obtaining threshold value >70 mg/dL,
    - at any time if occurrence of one or more symptoms of hypoglycemia (common presenting symptoms include nausea, confusion, tremor, sweating, palpitations, or hunger), sugar will be given to the participant and a blood glycemia test should be immediately performed and closely monitored.

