#### 8.5.3 Hospital discharge, D2

Before participant discharge from the hospital, the investigator or delegate will

- perform a physical exam and record vital signs,
- remind the participant
  - o to assess target knee pain [NRS] (based on the previous 24 hours) on a daily basis from D3 to the next visit date (D8),

- o to fill in the diary from D2 (after hospital discharge) up to the next visit (D8) to self-report adverse events and pain killer medication,
- give appointment for a virtual visit (phone call) at D4 ± 1d and for a face-to-face visit on D8 ± 2 days.

No specific physical limitation is recommended from the day after the injection.

In case of safety concerns after hospital discharge, the participant will be asked to call the investigator / to return to the hospital for an unscheduled safety control visit according to the investigator judgement.

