# Clinical safety laboratory evaluation

Individual results of laboratory tests from hematology, and chemistry that meet PCSA criteria to be defined in the SAP will be listed and summarized. Baseline, post-dose, and change from Baseline to post-dose laboratory data will be summarized. All clinical laboratory data will be listed.

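### SAP 12.7 leaves every unscheduled post-dose glucose out of the glycemia table and its PCSA count, and its change from baseline mixes glucometer and blood values

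*SAP*

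**What the plan says.** The glycemia part of SAP 12.7 aims at one value per scheduled time. Its rule for extra samples is "Additional samples vs. scheduled samples will not be analyzed, unless they are the baseline". Baseline is the last measure before injection, and for tied times: "If there are such two measures (same time, different method), then Blood will be selected". The table runs from baseline to 24 h in the vital signs layout of SAP 12.5, which gives the value, the absolute change from baseline and the PCSA frequency at each time. SAP 19 sets the glycemia PCSA strictly below 70 mg/dL. The D8 glucose goes to the chemistry tables.

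Protocol 8.5.2 requires extra tests. After a planned value at or below 70 mg/dL without symptoms, the site must "repeat the test each 30 min up to obtaining threshold value >70 mg/dL". On any symptom of hypoglycemia, "a blood glycemia test should be immediately performed and closely monitored". After discharge, Protocol 8.5.3 allows the participant with a safety concern "to return to the hospital for an unscheduled safety control visit".

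For laboratory changes, including glycemia, Protocol 3.2.1 defines the primary endpoint as "Mean changes number of PCSA, Percentage of participants with PCSA". Protocol 10.1.4 adds: "Individual results of laboratory tests from hematology, and chemistry that meet PCSA criteria to be defined in the SAP will be listed and summarized". It makes no exception for unscheduled samples.

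**The concern.** Hypoglycemia is a named risk of liraglutide, and glycemia PCSA and mean change are primary endpoints. The samples most likely to catch a low are those taken because a symptom occurred or a value was already low. The only exception to the exclusion is a sample that serves as baseline, so no unscheduled post-dose value can enter the table. The error has one direction: the count can only fall, and the depth of a low can only be understated.

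Triggered samples may well exist. Nausea is among the symptoms in Protocol 8.5.2 that call for an immediate test, and Protocol 2.3 reports nausea in 5 participants of cohort 3, the cohort on which the view that the MTD may have been reached rests. Event times and glucose values are not given, so the number of such samples is unknown.

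Separately, setting one baseline against two measuring methods can make a difference between glucometer and laboratory look like a change over time within a group.

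**Working it through.** The plan states no figure to reproduce here. The inputs are the glycemia schedule and rules in SAP 12.7, the PCSA limit in SAP 19, the triggered tests in Protocol 8.5.2, the DLT definition in Protocol 4.6.1, and the planned allocation of 6 active and 2 placebo in each of 4 cohorts.

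**(a) Which lows are left out**

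| Sample | In the table? | Consequence |
|---|---|---|
| Symptom-triggered test below 70 mg/dL | No | Participant uncounted unless a scheduled value is also below 70 |
| Repeat below 70 after a planned value of exactly 70 | No | Uncounted: the repeat trigger includes 70, the PCSA does not |
| Repeat after a planned value below 70 | No | Participant already counted; a lower value and the duration are lost |
| Any glucose after 24 h and before D8 | No | Uncounted: nothing is scheduled there |

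The DLT level is 2.5 mmol/L × 18.016 (standard conversion) = 45.0 mg/dL, within 2 days of injection. The last scheduled value before D8 (±2 days) is at 24 h, so the second day of that window holds none. The unscheduled stretch is 96 to 192 h: from (6 − 1) × 24 − 24 to (10 − 1) × 24 − 24.

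Gaps between scheduled times from injection to 24 h are 1, 1, 2, 2, 2, 2, 2, 4 and 8 h. As an illustration, assume an episode of length L with onset uniform over 0–24 h. The share of onsets with no scheduled time inside the episode is Σ max(0, gap − L) / 24:

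- L = 0.5 h: 19.5/24 = 81%
- L = 1 h: 15/24 = 62.5%
- L = 2 h: 8/24 = 33%
- L = 3 h: 6/24 = 25%

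Weight of one uncounted participant (planned numbers; exact Clopper-Pearson 95% intervals):

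- dose group of 6: 0/6 = 0% (0–45.9%) instead of 1/6 = 16.7% (0.4–64.1%)
- pooled placebo: 1/8 = 12.5% (0.3–52.7%)
- pooled active: 1/24 = 4.2% (0.1–21.1%)

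SAP 9.3 records a ninth participant in cohort 3, so actual denominators may differ slightly.

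**(b) Mixed methods**

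| Hours post-dose | 1 | 2 | 4 | 6 | 8 | 10 | 12 | 16 | 24 |
|---|---|---|---|---|---|---|---|---|---|
| Method | meter | blood | blood | meter | blood | meter | blood | blood | meter |

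This gives 4 meter and 5 blood times. A blood baseline mismatches 4 of 9; a meter baseline mismatches 5 of 9. Either is possible, since both methods are planned pre-dose and the flowchart in Protocol 1.2.2 allows a 4-hour window. The method switches in 6 of the 8 adjacent intervals (1–2, 4–6, 6–8, 8–10, 10–12 and 16–24 h).

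Let d be the meter-minus-laboratory offset and p the share of a group with a meter baseline.

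- Shift in mean change at meter times: d(1 − p)
- Shift at blood times: −dp
- Step at each switch: d(1 − p) − (−dp) = d, whatever p is
- Remainder against placebo: d × (p in the dose group − p in placebo), zero if the shares are equal

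The documents give neither d nor p. With assumed p = 2/6 and 1/8, the remainder is 0.208d: 1.0 mg/dL for d = 5, 2.1 for d = 10 and 3.1 for d = 15.

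**The case against.** The exclusion serves a list that picks one value per scheduled time, and restricting means by time to scheduled values is ordinary practice. That stands, and the fix keeps it.

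The excluded values are not lost. Protocol 10.1.4 and SAP 9 base the safety evaluation on individual values as well as summaries, Listing 16.2.16 covers glycemia, and hypoglycemia is an AESI with its own tables, rapid notification and DSMB review. The treatment-emergent period runs to 7 days, so it covers the second day of the DLT window. A symptomatic low is unlikely to go unreported. This limits the consequence but does not supply the count. The hypoglycemia AESI has no numeric limit, and under Protocol 8.1.4 and 11.3.1 a laboratory result becomes an AE only if judged clinically significant. An unscheduled value below 70 mg/dL not so judged would be listed but not summarized.

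Some routes are narrow: the planned value of exactly 70 is rare, and Protocol 8.5.3 does not say that glucose is taken at an unscheduled visit. PCSA by time point also applies to other parameters, and the lack of a table at the DLT level is not caused by this rule. These points are fair. The main route, a low seen only on a triggered test, does not depend on them.

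On part (b), an additive offset largely cancels against placebo, the absolute PCSA uses no baseline, and no significance test is planned. All of this is correct. The distortion is in the within-group course over time, and a footnote would disclose it without removing it.

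**Conclusion.** Both parts hold, and the SAP should be changed.

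Part (a): as written, the rule excludes every unscheduled post-dose glucose from the glycemia table and its PCSA count, against a primary endpoint expressed as a percentage of participants and a protocol statement that results meeting the criteria will be summarized. The number affected cannot be derived from the documents; the weight per participant is 16.7 percentage points in a group of six. No table in SAP 17 gives the lowest glucose per participant or counts values at the DLT level. The gap is confined to the numeric summary: the rule does not govern AESI or DLT classification.

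Part (b): the counts of 4 or 5 mismatched times out of 9, and 6 switches out of 8, follow directly from the schedule. The size in mg/dL depends on an offset the documents do not give. It appears in full within a group at each switch, and against placebo only in proportion to the difference in baseline method.

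**What to change.** - Keep scheduled values only for the means by time.
- From all post-injection glucose values, scheduled and unscheduled, add per participant: any value below 70 mg/dL; any value at or below 2.5 mmol/L within 2 days (the protocol's own DLT level); and the minimum. State that the exclusion of additional samples does not apply to these rows.
- Compute change from a method-matched pre-dose baseline: glucometer for 1, 6, 10 and 24 h; blood for 2, 4, 8, 12 and 16 h. Alternatively, present separate tables by method.

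The cost is SAP wording and a little programming. Both methods are already planned pre-dose, so no new data are needed. The hypoglycemia count may rise slightly. Because participants with symptoms are tested more often, the count from scheduled values should stay visible beside the any-value count. Change from baseline will be missing at some times for a participant who lacks one pre-dose method. If the database is already locked, SAP 6.2 allows these as additional analyses identified as such in the CSR.

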#### 9.3 Planned and Actual Treatment

In cohort 3 one participant was underdosed; the Sponsor decided (blinded review) to include one more participant to ensure 6 participants with the right active dose; consequently a ninth participant has been included to receive the same treatment as the underdosed participant. Therefore, at least one subject may have an actual treatment different from the planned one (if the underdosed subject did not receive placebo).

Participants who did not receive the planned treatment will be assigned, upon review of their actual treatment, to either of the following actual arm:

if the received treatment is one of the planned ones, or close enough, to the corresponding arm

otherwise, to an arm "4P004 unplanned"

Unless stated otherwise, analyses will be presented by actual arm.

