### Chemistry:

- Creatinine Clearance
- Potassium
- Chloride
- Sodium
- Calcium
- Alanine Aminotransferase
- Aspartate Aminotransferase
- Amylase
- Glucose (at Screening and Visit 3)

They will be presented like Vital Signs, but with one table for Hematology, one for Chemistry.

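### No planned table gives the percentage of participants with a glycemia PCSA, and the by-timepoint counts leave out symptom-triggered glucose tests

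*SAP*

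**What the plan says.** **Endpoint.** The laboratory part of the primary endpoints in Protocol 3.2.1 includes "glycemia, amylasemia, creatinin clearance) from D-7 to D8: Mean changes number of PCSA, Percentage of participants with PCSA". SAP 19 defines the glycemia PCSA as a value below 70 mg/dL, with no condition on change from baseline. Protocol 10.1.4 commits to both listing and summarizing the laboratory results that meet PCSA criteria.

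**Unscheduled tests.** Protocol 8.5.2 creates two kinds. When symptoms of hypoglycemia appear at any time in the stay, the text reads: "nausea, confusion, tremor, sweating, palpitations, or hunger), sugar will be given to the participant and a blood glycemia test should be immediately performed". No confirmed low value is needed first. When a planned measurement is low but the participant has no symptoms, the rule is: "glycemia is ≤ 70 mg/dL without clinical symptom repeat the test each 30 min", continuing until the value is above 70.

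**Analysis.** SAP 12.7 sets out how to obtain one glucose value per scheduled timepoint. Blood is preferred to the glucose meter when both exist, and "Additional samples vs. scheduled samples will not be analyzed, unless they are the baseline". The display is then fixed: "The values will be reported over time (Baseline, 1h Post-Dose to 24h Post-Dose) with the same template as Vital Signs". In that template (SAP 12.5), PCSA counts and percentages sit under each timepoint. The Chemistry list in SAP 12.7 takes glucose from Screening and Visit 3 only, so Tables 7.2 and 7.2.1 carry none of the in-hospital values. SAP 17 names no other glycemia table. SAP 18 provides a glycemia listing (16.2.16).

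**The concern.** The endpoint is a statement about people: how many participants had a low glucose in the observation window. A by-timepoint table answers a different question, namely how many were low at a given hour. Nothing in the planned output turns the second into the first.

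The post-dose samples that SAP 12.7 sets aside include those drawn because hypoglycemia was suspected. Protocol 4.2 names the drug's hypoglycemic properties among the risks that the design is meant to mitigate. At stake is the accuracy of one component of a primary safety endpoint, in groups so small that a single participant moves the figure visibly.

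**Working it through.** **1. Group sizes.** The plan's total is reproduced: 4 cohorts × (6 active + 2 placebo) = 32. Protocol 10.2 says this was not based on power, so there is no power figure to check. The planned denominators are 6 per dose group, 4 × 2 = 8 for pooled placebo and 4 × 6 = 24 for pooled active. SAP 9.3 adds that in cohort 3 "a ninth participant has been included to receive the same treatment as the underdosed participant", so one pooled denominator becomes 9 (placebo) or 25 (active), depending on that participant's arm.

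**2. Scheduled sampling.** The post-dose glycemia times in SAP 12.7 are 1, 2, 4, 6, 8, 10, 12, 16 and 24 h, which is nine timepoints. The successive gaps from injection are 1, 1, 2, 2, 2, 2, 2, 4 and 8 h. A low value that appears and recovers between 16 h and 24 h can be recorded only by an unscheduled test.

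**3. Who is counted under the SAP rule.**

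| Participant's only post-dose finding | Shown as a glycemia PCSA in a table? |
|---|---|
| Scheduled in-hospital value below 70 | Yes, at that timepoint in Table 7.3 |
| Selected Visit 3 value below 70 | Yes, in Table 7.2.1 only |
| Scheduled value exactly 70, a 30-minute repeat below 70 | No: 70 triggers repeats (≤ 70) but is not a PCSA (< 70), and the repeat is not analyzed |
| Scheduled values all 70 or above, symptom-triggered value below 70 | No: the test is an additional sample |

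**4. Size of one uncounted participant.** Effect = 1/n.

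| Group | Counted | Under the SAP rule | Difference (points) |
|---|---|---|---|
| Dose group, n = 6 | 1/6 = 16.7% | 0/6 = 0.0% | 16.7 |
| Pooled placebo, n = 8 | 1/8 = 12.5% | 0/8 = 0.0% | 12.5 (1/9 = 11.1 if n = 9) |
| Pooled active, n = 24 | 1/24 = 4.2% | 0/24 = 0.0% | 4.2 (1/25 = 4.0 if n = 25) |

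The exact (Clopper-Pearson) 95% intervals are 0 to 45.9% for 0/6 and 0.4 to 64.1% for 1/6. They overlap heavily, so the point concerns a correct count and not a change in inference.

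**5. The missing row, without any unscheduled test.** Suppose two scheduled timepoints each show 1/6 = 16.7%. If the same participant was low twice, the participant-level result is 1/6 = 16.7%. If two participants were low once each, it is 2/6 = 33.3%. Table 7.3 looks the same in both cases.

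**The case against.** The strongest reply is that the exclusion is only a selection rule for a by-time table, where an off-schedule value has no row. A fixed schedule also keeps detection equal between arms. Nausea is on the symptom list that triggers testing, and Protocol 2.3 describes it as a very common reaction to liraglutide, so extra tests would probably cluster in the active groups. This stands for means and changes, and Table 7.3 should keep the rule. It does not supply the participant-level percentage.

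It can also be said that Protocol 3.2.1 does not state whether its percentage is per timepoint or over the whole window. That is true. But the wording, "Mean changes number of PCSA, Percentage of participants with PCSA", is attached to a window from D-7 to D8, and no planned table covers that window for glycemia. The table shells are abbreviated, yet no text or table title mentions an any-time row.

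The AESI tables deserve credit. Hypoglycemia is an AESI with no severity condition, and SAP 12.2.4 tabulates treatment-emergent AESIs as participants and events by dose group. A symptomatic low may well appear there. That depends on the investigator reporting it, and no glucose cut-off is stated for the AESI, so it is not the same measure as a value below 70 mg/dL. The DLT cut-off of 2.5 mmol/L (about 45 mg/dL, from 2.5 × 18.016) is far lower.

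Finally, SAP 9.2 promises analysis of the maximum available observed data, but the specific rule in SAP 12.7 governs glycemia.

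**Conclusion.** The point holds as a minor one. The planned tables do not give the glycemia PCSA percentage by participant, and the stated rule can show 0/6 at every timepoint when a participant did have a value below 70 mg/dL. Each such participant is worth 16.7 points in a dose group of 6. This assumes that the SAP 12.7 rule is applied as written and that the participant's only low value is one of the two uncounted kinds. The documents do not show how often that occurs.

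A reader might infer more than the documents support:

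- **That low values are hidden or participants are less protected.** All laboratory data are listed, SAP 9 bases the safety evaluation on individual values as well as summaries, and the AESI, DLT and stopping rules are untouched.
- **That dropping a repeat lower than a scheduled value already below 70 changes the percentage.** It does not, because that participant is already a PCSA.
- **That the nausea reported for 5 cohort 3 participants (Protocol 2.3) implies many missed lows.** No onset time, arm or glucose value is given for them.
- **That mean glucose is biased.** Size and direction are unknown, and no meal control is described.
- **That the two-timepoint example can be stretched over all nine timepoints.** That would give only an arithmetic bound, with no evidence about this trial.

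**What to change.** Keep the care rule in Protocol 8.5.2 and keep Table 7.3 on scheduled values. In SAP 12.7 add, by dose group:

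1. n (%) of participants with any post-dose glucose below 70 mg/dL up to D8;
2. a summary of each participant's minimum post-dose glucose.

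Show each in two versions side by side: scheduled values only, and all values including symptom-triggered and 30-minute repeat tests. Keep the existing preference for blood when blood and glucose meter are paired at the same timepoint, so that a meter reading at Visit 3 does not override its paired blood value.

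The cost is two summary rows in two versions, using results of tests the protocol already orders. The downside is unequal detection: participants with symptoms are tested more often, so the all-values version can favour finding lows in them. The scheduled-only version beside it lets the reader judge that. If the SAP can no longer be changed, SAP 3 and 6.2 allow these rows in the CSR, identified as additional to the plan.
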